7. ADVERSE EVENTS: LIST AND REPORTING REQUIREMENTS

Adverse event (AE) monitoring and reporting is a routine part of every clinical trial. The following list of AEs (Section 7.1) and the characteristics of an observed AE (Section 7.2) will

determine whether the event requires expedited reporting via the CTEP Adverse Event Reporting System (CTEP-AERS) **in addition** to routine reporting. Adverse events will be assessed at each visit by the clinical trial personnel.

7.1 Comprehensive Adverse Events and Potential Risks List (CAEPR)

The Comprehensive Adverse Event and Potential Risks list (CAEPR) provides a single list of reported and/or potential adverse events (AE) associated with an agent using a uniform presentation of events by body system. In addition to the comprehensive list, a subset of AEs, the Specific Protocol Exceptions to Expedited Reporting (SPEER), appears in a separate column and is identified with **bold** and *italicized* text. The SPEER is a list of events that are protocol-specific exceptions to expedited reporting to NCI (except as noted below). Refer to the 'CTEP, NCI Guidelines: Adverse Event Reporting Requirements' http://ctep.cancer.gov/protocolDevelopment/adverse_effects.htm for further clarification.

The CAEPR may not provide frequency data; if not, refer to the Investigator's Brochure for this information.

NOTE: The highest grade currently reported is noted in parentheses next to the AE in the SPEER. Report **ONLY** AEs higher than this grade expeditiously. If this CAEPR is part of a combination protocol using multiple investigational agents and has an AE listed on different SPEERs, use the lower of the grades to determine if expedited reporting is required.

7.1.1 CAEPRs for CTEP IND Agent

7.1.1.1 CAEPR for AT13387 (onalespib)

Below is the CAEPR for AT13387 (Onalespib). *Frequency is provided based on 119 patients.*

NOTE: Report AEs on the SPEER **ONLY IF** they exceed the grade noted in parentheses next to the AE in the SPEER. If this CAEPR is part of a combination protocol using multiple investigational agents and has an AE listed on different SPEERs, use the lower of the grades to determine if expedited reporting is required.

IMPORTANT: Below is the CAEPR list with the current version of CTCAE terms (version 5.0).

Adverse Events with Possible Relationship to AT13387 (Onalespib) (CTCAE 5.0 Term) [n= 119]			Specific Protocol Exceptions to Expedited Reporting (SPEER)
Likely (>20%)	Less Likely (<=20%)	Rare but Serious (<3%)	
BLOOD AND LYMPHATIC SYSTEM DISORDERS			
Anemia			Anemia (Gr 2)
EYE DISORDERS			
	Blurred vision		
	Vision decreased		Vision decreased (Gr 2)
GASTROINTESTINAL DISORDERS			
	Abdominal pain		Abdominal pain (Gr 2)
	Constipation		Constipation (Gr 2)
Diarrhea			Diarrhea (Gr 2)
	Dry mouth		Dry mouth (Gr 2)
	Dyspepsia		Dyspepsia (Gr 2)
	Flatulence		Flatulence (Gr 2)
	Gastrointestinal hemorrhage ²		
	Hemorrhoids		Hemorrhoids (Gr 2)
Nausea			Nausea (Gr 2)
	Vomiting		Vomiting (Gr 2)
GENERAL DISORDERS AND ADMINISTRATION SITE CONDITIONS			
	Edema limbs		
Fatigue			Fatigue (Gr 2)
	Fever ³		Fever³ (Gr 2)
Injection site reaction ⁴			Injection site reaction⁴ (Gr 2)
	Malaise		Malaise (Gr 2)
INFECTIONS AND INFESTATIONS			
	Infection ⁵		Infection⁵ (Gr 2)
INJURY, POISONING AND PROCEDURAL COMPLICATIONS			
	Infusion related reaction ³		Infusion related reaction³ (Gr 2)
INVESTIGATIONS			
	Alanine aminotransferase increased		Alanine aminotransferase increased (Gr 2)
	Alkaline phosphatase increased		Alkaline phosphatase increased (Gr 2)
	Aspartate aminotransferase increased		Aspartate aminotransferase increased (Gr 2)
	CPK increased		CPK increased (Gr 2)
	Electrocardiogram QT corrected interval prolonged		
	Lymphocyte count decreased		Lymphocyte count decreased (Gr 2)
	Platelet count decreased		Platelet count decreased (Gr 2)
	Weight loss		Weight loss (Gr 2)
	White blood cell decreased		
METABOLISM AND NUTRITION DISORDERS			
	Anorexia		Anorexia (Gr 2)
	Dehydration		Dehydration (Gr 2)
	Hypocalcemia		Hypocalcemia (Gr 2)
	Hypokalemia		
	Hypomagnesemia		

Adverse Events with Possible Relationship to AT13387 (Onalespib) (CTCAE 5.0 Term) [n= 119]			Specific Protocol Exceptions to Expedited Reporting (SPEER)
Likely (>20%)	Less Likely (<=20%)	Rare but Serious (<3%)	
	Hyponatremia		Hyponatremia (Gr 2)
MUSCULOSKELETAL AND CONNECTIVE TISSUE DISORDERS			
	Muscle cramp		Muscle cramp (Gr 2)
	Myalgia		Myalgia (Gr 2)
NERVOUS SYSTEM DISORDERS			
	Dizziness		Dizziness (Gr 2)
	Dysgeusia		
	Headache		Headache (Gr 2)
PSYCHIATRIC DISORDERS			
	Insomnia		Insomnia (Gr 2)
RESPIRATORY, THORACIC AND MEDIASTINAL DISORDERS			
	Cough		Cough (Gr 2)
	Dyspnea		Dyspnea (Gr 2)
	Hiccups		Hiccups (Gr 2)
SKIN AND SUBCUTANEOUS TISSUE DISORDERS			
	Dry skin		Dry skin (Gr 2)
	Hyperhidrosis ³		Hyperhidrosis³ (Gr 2)
	Rash acneiform		
	Rash maculo-papular		Rash maculo-papular (Gr 2)
VASCULAR DISORDERS			
	Flushing		Flushing (Gr 2)

¹This table will be updated as the toxicity profile of the agent is revised. Updates will be distributed to all Principal Investigators at the time of revision. The current version can be obtained by contacting [contact]. Your name, the name of the investigator, the protocol and the agent should be included in the e-mail.

²Gastrointestinal hemorrhage includes Anal hemorrhage, Cecal hemorrhage, Colonic hemorrhage, Duodenal hemorrhage, Esophageal hemorrhage, Esophageal varices hemorrhage, Gastric hemorrhage, Hemorrhoidal hemorrhage, Ileal hemorrhage, Intra-abdominal hemorrhage, Jejunal hemorrhage, Lower gastrointestinal hemorrhage, Oral hemorrhage, Pancreatic hemorrhage, Rectal hemorrhage, Retroperitoneal hemorrhage, and Upper gastrointestinal hemorrhage under the GASTROINTESTINAL DISORDERS SOC.

³Infusion-related reactions may include, tachycardia/bradycardia, hypotension/hypertension, flushing, chills, fever, hyperhidrosis, itching, rigors, and abdominal cramps.

⁴Injection site reaction may include injection site irritation, injection site pain, injection site inflammation or redness, or erythema.

⁵Infection may include all 75 sites of infection under the INFECTIONS AND INFESTATIONS SOC.

Adverse events reported on AT13387 (Onalespib) trials, but for which there is insufficient evidence to suggest that there was a reasonable possibility that AT13387 (Onalespib) caused the adverse event:

BLOOD AND LYMPHATIC SYSTEM DISORDERS - Febrile neutropenia

CARDIAC DISORDERS - Cardiac disorders - Other (atrioventricular block NOS); Left ventricular systolic dysfunction; Palpitations

EYE DISORDERS - Dry eye; Eye disorders - Other (color distortion); Eye disorders - Other (diplopia); Eye disorders - Other (halos); Eye disorders - Other (loss of visual acuity during changes in ambient light levels); Eye disorders - Other (tunnel vision); Eye disorders - Other (visual color darkening); Eye disorders - Other (visual disturbances); Eye pain; Flashing lights; Floaters; Keratitis; Night blindness; Papilledema; Photophobia; Retinopathy

GASTROINTESTINAL DISORDERS - Colitis; Mucositis oral; Oral dysesthesia; Oral pain; Salivary duct inflammation

GENERAL DISORDERS AND ADMINISTRATION SITE CONDITIONS - Chills³; Flu like symptoms

HEPATOBIILIARY DISORDERS - Hepatic hemorrhage

INVESTIGATIONS - Activated partial thromboplastin time prolonged; Blood bilirubin increased; Creatinine increased; Ejection fraction decreased; Neutrophil count decreased

METABOLISM AND NUTRITION DISORDERS - Hyperglycemia; Hypoalbuminemia; Hypophosphatemia

MUSCULOSKELETAL AND CONNECTIVE TISSUE DISORDERS - Back pain; Bone pain; Generalized muscle weakness

NERVOUS SYSTEM DISORDERS - Seizure; Syncope; Tremor

PSYCHIATRIC DISORDERS - Anxiety

RENAL AND URINARY DISORDERS - Acute kidney injury; Proteinuria

RESPIRATORY, THORACIC AND MEDIASTINAL DISORDERS - Pneumonitis

SKIN AND SUBCUTANEOUS TISSUE DISORDERS - Palmar-plantar erythrodysesthesia syndrome; Pruritus; Skin hyperpigmentation

VASCULAR DISORDERS - Hypertension³

Note: AT13387 (Onalespib) in combination with other agents could cause an exacerbation of any adverse event currently known to be caused by the other agent, or the combination may result in events never previously associated with either agent.

7.2 Adverse Event Characteristics

- **CTCAE term (AE description) and grade:** The descriptions and grading scales found in the revised NCI Common Terminology Criteria for Adverse Events (CTCAE) version 5.0 should be utilized for AE reporting. All appropriate treatment areas should have access to a copy of the current CTCAE version. A copy of the CTCAE versions can be downloaded from the CTEP web site:
http://ctep.cancer.gov/protocolDevelopment/electronic_applications/ctc.htm.
- **For expedited reporting purposes only:**
 - AEs for the agent that are ***bold and italicized*** in the CAEPR (*i.e.*, those listed in the SPEER column, Section 7.1.1) should be reported through CTEP-AERS only if the grade is above the grade provided in the SPEER.
 - Other AEs for the protocol that do not require expedited reporting are outlined in section 7.3.4.
- **Attribution of the AE:**
 - Definite – The AE *is clearly related* to the study treatment.
 - Probable – The AE *is likely related* to the study treatment.
 - Possible – The AE *may be related* to the study treatment.
 - Unlikely – The AE *is doubtfully related* to the study treatment.
 - Unrelated – The AE *is clearly NOT related* to the study treatment.

7.3 Expedited Adverse Event Reporting

- 7.3.1 Expedited AE reporting for this study must use CTEP-AERS (CTEP Adverse Event Reporting System), accessed via the CTEP Web site (<https://eapps-ctep.nci.nih.gov/ctepaers>). The reporting procedures to be followed are presented in the “NCI Guidelines for Investigators: Adverse Event Reporting Requirements for DCTD (CTEP and CIP) and DCP INDs and IDEs” which can be downloaded from the CTEP Web site http://ctep.cancer.gov/protocolDevelopment/electronic_applications/adverse_events.htm. These requirements are briefly outlined in the tables below (Section 7.3.3).

In the rare occurrence when Internet connectivity is lost, a 24-hour notification is to be made to CTEP by telephone at [contact]. Once Internet connectivity is restored, the 24-hour notification phoned in must be entered electronically into CTEP-AERS by the original submitter at the site.

7.3.2 Distribution of Adverse Event Reports

CTEP-AERS is programmed for automatic electronic distribution of reports to the following individuals: Principal Investigator and Adverse Event Coordinator(s) (if applicable) of the Corresponding Organization or Lead Organization, the local treating physician, and the Reporter and Submitter. CTEP-AERS provides a copy feature for other e-mail recipients.

The Coordinating Center of the Corresponding Organization is responsible for submitting to the CTSU documentation of AEs that they deem reportable for posting on the CTSU protocol web page and inclusion on the CTSU bi-monthly broadcast.

7.3.3 Expedited Reporting Guidelines

Use the NCI protocol number and the protocol-specific patient ID assigned during trial registration on all reports.

Note: A death on study requires both routine and expedited reporting, regardless of causality. Attribution to treatment or other cause must be provided.

Death due to progressive disease should be reported as Grade 5 “Disease progression” in the system organ class (SOC) “General disorders and administration site conditions. Evidence that the death was a manifestation of underlying disease (e.g., radiological changes suggesting tumor growth or progression: clinical deterioration associated with a disease process) should be submitted.

Phase 1 and Early Phase 2 Studies: Expedited Reporting Requirements for Adverse Events that Occur on Studies under an IND/IDE within 30 Days of the Last Administration

of the Investigational Agent/Intervention ^{1,2}

FDA REPORTING REQUIREMENTS FOR SERIOUS ADVERSE EVENTS (21 CFR Part 312)

NOTE: Investigators **MUST** immediately report to the sponsor (NCI) **ANY** Serious Adverse Events, whether or not they are considered related to the investigational agent(s)/intervention (21 CFR 312.64)

An adverse event is considered serious if it results in **ANY** of the following outcomes:

- 1) Death
- 2) A life-threatening adverse event
- 3) An adverse event that results in inpatient hospitalization or prolongation of existing hospitalization for ≥ 24 hours
- 4) A persistent or significant incapacity or substantial disruption of the ability to conduct normal life functions
- 5) A congenital anomaly/birth defect.
- 6) Important Medical Events (IME) that may not result in death, be life threatening, or require hospitalization may be considered serious when, based upon medical judgment, they may jeopardize the patient or subject and may require medical or surgical intervention to prevent one of the outcomes listed in this definition. (FDA, 21 CFR 312.32; ICH E2A and ICH E6).

ALL SERIOUS adverse events that meet the above criteria **MUST** be immediately reported to the NCI via electronic submission within the timeframes detailed in the table below.

Hospitalization	Grade 1 and Grade 2 Timeframes	Grade 3-5 Timeframes
Resulting in Hospitalization ≥ 24 hrs	10 Calendar Days	24-Hour 5 Calendar Days
Not resulting in Hospitalization ≥ 24 hrs	Not required	

NOTE: Protocol specific exceptions to expedited reporting of serious adverse events are found in the Specific Protocol Exceptions to Expedited Reporting (SPEER) portion of the CAEPR.

Expedited AE reporting timelines are defined as:

- “24-Hour; 5 Calendar Days” - The AE must initially be submitted electronically within 24 hours of learning of the AE, followed by a complete expedited report within 5 calendar days of the initial 24-hour report.
- “10 Calendar Days” - A complete expedited report on the AE must be submitted electronically within 10 calendar days of learning of the AE.

¹Serious adverse events that occur more than 30 days after the last administration of investigational agent/intervention and have an attribution of possible, probable, or definite require reporting as follows:

Expedited 24-hour notification followed by complete report within 5 calendar days for:

- All Grade 3, 4, and Grade 5 AEs

Expedited 10 calendar day reports for:

- Grade 2 AEs resulting in hospitalization or prolongation of hospitalization

²For studies using PET or SPECT IND agents, the AE reporting period is limited to 10 radioactive half-lives, rounded UP to the nearest whole day, after the agent/intervention was last administered. Footnote “1” above applies after this reporting period.

Effective Date: May 5, 2011

7.3.4 Additional Protocol-Specific Expedited Adverse Event Reporting Exclusions

For this protocol only, the AEs/grades listed below do not require expedited reporting via CTEP-AERS. However, they still must be reported through the routine reporting mechanism (Section 7.4):

CTCAE SOC	Adverse Event	Grade	Hospitalization/ Prolongation of Hospitalization	Attribution	Comments
Investigations	Lymphocyte count decreased	Any			
Investigations	INR increased, aPTT prolonged	2			
Skin and subcutaneous tissue disorders	Alopecia	Any			
Metabolism and nutrition disorders	Hyponatremia, Hypophosphatemia, Hypokalemia, Hypomagnesemia, Hypoalbuminemia, Hyperglycemia, Hyperuricemia	2			
Blood and lymphatic system disorders	Anemia	2			

7.4 Routine Adverse Event Reporting

All Adverse Events **must** be reported in routine study data submissions. **AEs reported expeditiously through CTEP-AERS must also be reported in routine study data submissions.**

Adverse event data collection and reporting, which are required as part of every clinical trial, are done to ensure the safety of patients enrolled in the studies as well as those who will enroll in future studies using similar agents. AEs are reported in a routine manner at scheduled times during the trial using Medidata Rave. For this trial the Adverse Event CRF is used for routine AE reporting in Rave.

7.5 Secondary Malignancy

A *secondary malignancy* is a cancer caused by treatment for a previous malignancy (e.g., treatment with investigational agent/intervention, radiation or chemotherapy). A secondary malignancy is not considered a metastasis of the initial neoplasm.

CTEP requires all secondary malignancies that occur following treatment with an agent under an NCI IND/IDE be reported expeditiously via CTEP-AERS. Three options are available to describe the event:

- Leukemia secondary to oncology chemotherapy (e.g., acute myelocytic leukemia [AML])
- Myelodysplastic syndrome (MDS)
- Treatment-related secondary malignancy

Any malignancy possibly related to cancer treatment (including AML/MDS) should also be reported via the routine reporting mechanisms outlined in each protocol.

7.6 Second Malignancy

A second malignancy is one unrelated to the treatment of a prior malignancy (and is **NOT** a metastasis from the initial malignancy). Second malignancies require **ONLY** routine AE reporting unless otherwise specified.

8. PHARMACEUTICAL INFORMATION

8.1 Drug Information

8.1.1 AT13387 (onalespib) (NSC 749712)

The NCI does not provide a pharmacy manual. All drug information and preparation guidelines are provided below.

Chemical Name:	(2,4-dihydroxy-5-isopropyl-phenyl)-[5-(4-methyl-piperazin-1-ylmethyl)-1,3-dihydro-isoindol-2-yl]-methanone, L -lactic acid salt
Other Name:	AT13387 (onalespib)AU, AT13387 (onalespib)
Classification:	Heat shock protein 90 (HSP90) inhibitor
Molecular Formula:	C ₂₄ H ₃₁ N ₃ O ₃ .C ₃ H ₆ O ₃ M.W.: 499.61
Mode of Action:	AT13387 (onalespib) is a small molecule inhibitor of HSP90, an enzyme believed to be responsible for supporting malignant transformation of normal cells to tumor cells. HSP90 acts as a “molecular chaperone,” stabilizing and preventing the breakdown of key cancer forming (oncogenic) proteins.
How Supplied:	AT13387 (onalespib) is supplied by Astex Pharmaceuticals Inc. and distributed by CTEP, NCI as a 265 mg free base equivalent (as the L -lactic acid salt) vial. The formulation is a sterile white to off-white lyophilized powder with pH 5.0 (red cap vial).
Preparation:	
Reconstitute the 265-mg lyophilized powder with 10 mL of Sterile Water for Injection (SWFI) resulting in 25.7 mg/mL concentration (10.3 mL total volume). A sticky mass will be formed. Vigorously shake the vial. Agitate until the contents are fully dissolved (about 5 minutes). Leave the diluted vial at ambient temperature for 15-30 minutes to allow any foam to dissipate. If not used immediately, store the reconstituted vial(s) at 2^o to 8^o C to not exceed 8 hours.
 
Withdraw the calculated dose of AT13387 and further dilute it in 250 mL of D5W or 0.9% NS. The prepared IV solution is compatible in PVC or non-PVC infusion bags.
 
Store the prepared IV solution at 2^o to 8^o C (up to 8 hours) if not used immediately. When removed from the refrigerator, allows the prepared IV solution to sit at room temperature between 15 to 30 minutes before

	administering to patients. The prepared IV solution must be used within 8 hours -i.e., from the time the drug vial is diluted to the time the IV administration is complete. Protection from light during the infusion period is not required.
Storage:	Store the intact vials at 15 ⁰ to 25°C (59 to 77°F). Protect from light. If a storage temperature excursion is identified, promptly return AT13387 to 15 ⁰ to 25°C (59 to 77°F) and quarantine the supplies. Provide a detailed report of the excursion (including documentation of temperature monitoring and duration of the excursion) to [contact] for determination of suitability.
Stability:	Shelf life surveillance of the intact vials is ongoing.
Route of administration:	Intravenous
Method of administration:	Infuse over 1 hour through a central line or a well-defined peripheral vein. If using a peripheral line, be sure to aspirate venous blood prior to starting the infusion. The IV infusion does not require a 0.2 micron in-line filter. Check the infusion site every 15 minutes and change the site of infusion should evidence of swelling or discoloration is observed. If patient experiences pain along the infusion site, slow the infusion rate (i.e. > 1 hour duration) and/or infuse D5W through a “Y” connector. The additional volume of D5W dilutes AT13387 (onalespib) concentration at the local site of the infusion and alleviates the irritation.
Potential Drug Interactions:	AT13387 (onalespib) is a substrate of UGT with a relatively low affinity for UGT isoforms. In vitro data demonstrate that AT13387 (onalespib) is a weak inhibitor of UGT1A1, UGT1A3 and UGT1A9. AT13387 (onalespib) is also a weak inhibitor of CYP1A2, -3A4, -2D6, -2C9 and -2C19. AT13387 (onalespib) metabolizes primary via the glucuronidation, sulphation and N-oxidation. Pre-clinical studies suggest that AT13387 (onalespib) is a substrate of P-gp, the efflux ratios was above 2 (ranging from 3.4 to 4.6); a moderate inhibitor of BCRP (35.9% +/- 2%, p=0.0001) and P-gp (31.3% +/- 1.2%, p= 0.0009), and a strong inhibitor of MATE1 (94.6% +/- 0.2%, p=0.0001) and MATE2-K (91.2% +/- 1.2%, p= 0.0002).
Patient Care Implications:	There are no genotoxicity, carcinogenicity, developmental and reproductive studies conducted with AT13387 (onalespib). Women of childbearing potential should not become pregnant or breastfeed and men should not father a child during the study. All subjects must use acceptable contraceptive measures during the treatment of AT13387 (onalespib) and 3 months after the last dose of the investigational drug. Local infusion-related irritation and systemic infusion reactions may occur during or shortly after the administration of AT13387 (onalespib). The local infusion adverse events are a formulation-related (pH of current formulation is 5.0). Systemic adverse events (e.g.; flushing, itching, rigors, chills, nausea, tachycardia/bradycardia, dizziness) are reversible. If that occurs, slow the infusion rate and/or hydrate with D5W. Premedication with dexamethasone, antihistamine and 5HT3 antagonists can also be given.

	Avoid extravasation. For local irritation, apply cold compress or topical pain medication.
--	--

A list of the adverse events and potential risks associated with AT13387 (onalespib) administered in this study can be found in Section 7.1.

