3.1.6 Life expectancy of greater than 3 months

3.1.7 Patients must have normal organ and marrow function, and electrolyte balance (allowing for repletion) as defined below:

- absolute neutrophil count $\geq 1,000/\text{mcL}$
- platelets $\geq 75,000/\text{mcL}$, unless due to marrow involvement by lymphoma in which case a platelet count of $\geq 30,000/\text{mcL}$ will be used
- total bilirubin $\leq 1.5x$ ULN, unless due to Gilbert's syndrome or hemolysis, in which case $\leq 3.0x$ ULN is allowed.
- AST(SGOT)/ALT(SGPT) $\leq 3.0 \times$ institutional upper limit of normal
- creatinine $\leq 1.5x$ ULN or a creatinine clearance $\geq 50 \text{ mL/min}/1.73 \text{ m}^2$ for patients with creatinine levels above institutional normal.
- Potassium above the institutional lower limit of normal (supplementation to meet this is allowed)
- Magnesium above the institutional lower limit of normal (supplementation to meet this is allowed)

3.1.8 HIV+ patients are eligible for the trial provided they meet the other study criteria in addition to the following:

- CD4+ T-cells $\geq 250/\text{mm}^3$
- HIV sensitive to antiretroviral therapy
- Zidovudine not allowed
- Long term survival anticipated on the basis of HIV alone were it not for the lymphoma
- No concurrent AIDS-defining illness other than the lymphoma

- 3.1.9 The effects of AT13387 (onalespib) on the developing human fetus are unknown. For this reason, women of child-bearing potential and men must agree to use adequate contraception (hormonal or barrier method of birth control; abstinence) prior to study entry, for the duration of study participation, and for 4 months after the completion of AT13387 (onalespib) administration. Should a woman become pregnant or suspect she is pregnant while she or her partner is participating in this study, she should inform her treating physician immediately. Men treated or enrolled on this protocol must also agree to use adequate contraception prior to the study, for the duration of study participation, and 4 months after completion of AT13387 (onalespib) administration.

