5.2.4 Antiemetics

Antiemetics will not be administered routinely prior to receiving AT13387 (onalespib). However, if a patient develops nausea/vomiting, anti-emetics such as but not limited to prochlorperazine, metochlopramide, or aprepitant may be given. 5-HT₃ antagonists like ondansetron are not allowed given their prolonging effecting on the QTc interval. In addition, if a patient develops nausea and/or vomiting at any dose level that is Grade 2 or greater, anti-emetics may be instituted prophylactically at the discretion of the investigator. Nausea and vomiting will be considered refractory if it does not resolve to \leq Grade 1 with treatment with combination antiemetics within 48 hours.

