5.2.12 QTc prolonging drugs

Every attempt will be made to avoid medications that have been associated with QT interval prolongation or Torsades de Pointes (see Appendix B). Antiemetics and diphenhydramine will be permitted on study with the exception of 5-HT₃ antagonists like ondansetron. Patients who are stable on antidepressants known to prolong QTc will be permitted to continue on their medication at the discretion of the Principal Investigator, provided the QTc at enrollment meets eligibility criteria.

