5.5 Criteria for Removal from Study

Patients will discontinue study treatment when any of the criteria listed in Section 5.3 applies. Patients will be removed from study after the follow-up period outlined in Section 5.4, or if they decide to withdraw from the study. The reason for study removal and the date the patient was removed must be documented in the Case Report Form.

In the event of unusual or life-threatening complications, participating investigators must immediately notify the Principal Investigator [name] at [contact] or [contact] (page through operator).

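### Section 8.1.1 permits a drug class that Sections 5.2.4 and 5.2.12 prohibit for QTc reasons, and sets a post-treatment contraception period 1 month shorter than Section 3.1.9

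*Combined protocol and SAP*

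**What the plan says.** **5-HT3 antagonists.** The Patient Care Implications row of Section 8.1.1 deals with systemic infusion reactions. It advises slowing the infusion or hydrating, and adds: "Premedication with dexamethasone, antihistamine and 5HT3 antagonists can also be given". Section 5.2.4 says of the 5-HT3 class: "antagonists like ondansetron are not allowed given their prolonging effecting on the QTc interval". Section 5.2.12 repeats the bar: "Antiemetics and diphenhydramine will be permitted on study with the exception of" that class. Section 5.2.7, which also covers infusion reactions, lists acetaminophen, diphenhydramine, hydrocortisone and optional famotidine, or equivalents. It names no 5-HT3 antagonist.

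**Contraception.** Section 8.1.1 says: "All subjects must use acceptable contraceptive measures during the treatment of AT13387 (onalespib) and 3 months after the last dose of the investigational drug". Section 3.1.9 requires contraception of women of child-bearing potential and men before study entry and "for the duration of study participation, and for 4 months after the completion of AT13387 (onalespib) administration". It repeats the period for men: "and 4 months after completion of AT13387 (onalespib) administration".

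**Standing of Section 8.1.1.** The section opens by stating that there is no pharmacy manual, and that "All drug information and preparation guidelines are provided below".

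**The concern.** Because no pharmacy manual exists, a pharmacist or infusion nurse would reasonably look to Section 8.1.1 for drug handling and reaction management. In both places it is the more permissive text, so a site that follows it exactly gives less protection than Sections 3 and 5 require.

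Use of the barred class is plausible. Nausea is one of the systemic reactions that Section 8.1.1 names, and Section 2.2.1.2 reports nausea in 53% of patients given onalespib and vomiting in 32%. The same section reports hypokalemia in 15%, and the adverse event list in Section 7.1.1.1 includes QTc prolongation as possibly related to the drug.

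On contraception, Section 3.1.9 calls the fetal effects unknown, and Section 8.1.1 states that no genotoxicity, developmental or reproductive studies have been done. A patient advised from Section 8.1.1 could stop contraception before Section 3.1.9 allows.

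**Working it through.** The check is a comparison of current sections. No sample size, power or error rate is involved, and there is no planned figure to reproduce.

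**Step 1: 5-HT3 antagonists**

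| Section | Setting | Status of the class |
|---|---|---|
| 8.1.1 | Premedication, systemic infusion reactions | May be given |
| 5.2.4 | Antiemetics | Not allowed, QTc reason given |
| 5.2.12 | QTc-prolonging drugs | Excepted from permitted antiemetics |
| 5.2.7 | Premedication after an infusion reaction | Not listed; list open to equivalents |

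Neither 5.2.4 nor 5.2.12 limits the bar by reason for use, and neither exempts infusion reactions. Section 8.1.1 does not refer back to them, and the available text has no order of precedence. Section 8.1.1 therefore permits what two other sections forbid. Section 5.2.7 is not a further conflict, because its list is open.

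**Step 2: contraception**

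| Section | Who | Period after the last onalespib dose |
|---|---|---|
| 8.1.1 | All subjects | 3 months |
| 3.1.9 | Women of child-bearing potential, and men | 4 months |

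Gap = 4 − 3 = 1 month. Sections 5.1 and 5.3 require all patients to be off treatment by May 31, 2020. For a last dose on that date, Section 8.1.1 would end contraception about August 31, 2020, and Section 3.1.9 no earlier than about September 30, 2020.

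**Step 3: what bounds the risk**

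- The premedication in Section 8.1.1 is optional. A site that applies the stricter rule in each case complies with every section.
- Section 13.1 states that enrollment closed as of October 2019. The May 31, 2020 limit caps any further premedication.
- Section 3.2.11 excludes patients with consistently prolonged QTc, and Section 5.1.1 sets potassium and magnesium criteria before each treatment week.
- Section 2.2.1.2 reports no QTcF effect on twice-weekly dosing up to 120 mg/m². It reports an increase of 10–15 ms on once-weekly 220–310 mg/m², and concludes that a clinically relevant effect is unlikely. Neither schedule is this trial's 160 mg/m² on two consecutive days per week, so the reassurance is indirect.

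**The case against.** The strongest case on the other side is that these are two drafting mismatches with little consequence. Concomitant medication has its own section, 5.2, which states the bar twice and gives the reason once; Section 8.1.1 stands in mainly for a pharmacy manual. What patients were told about contraception depends largely on the consent form, and the drug handout is in Appendix B. Neither was available to check. No endpoint or analysis is touched.

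Most of this stands as a limit on size. It does not remove the conflict: Section 8.1.1 is presented as the source of drug information, and its wording on both points contradicts current rules. It does mean that actual misuse, or wrong advice to patients, cannot be inferred.

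A reader might also infer a contraception gap well beyond 1 month. Section 3.1.9 counts study participation, Section 5.4 allows follow-up of up to 1 year, and Section 5.5 says: "Patients will be removed from study after the follow-up period outlined in Section 5.4". The documents do not support that inference. Section 3.1.9 does not define study participation. Section 8.1.1 also says that women should not become pregnant and men should not father a child during the study. If the study is read to run through follow-up, both sections already call for avoiding pregnancy throughout it.

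**Conclusion.** The point holds. Section 8.1.1 conflicts with Sections 5.2.4 and 5.2.12 on 5-HT3 antagonists, and with Section 3.1.9 on contraception after treatment. The certain size of the contraception conflict is 1 month. The number of patients affected by either conflict cannot be derived, because the documents do not give the number enrolled, the number still on treatment, or how many would receive such premedication.

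This is an internal inconsistency in safety instructions, worth correcting because it concerns a prohibited drug class and pregnancy prevention. The risk is limited for the reasons given in Step 3 of the working, and no statistical result changes. The conclusion assumes that no page missing from the available text, such as Appendix B or the consent form, sets an order of precedence between the sections.

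**What to change.** Change two sentences in the Patient Care Implications row of Section 8.1.1.

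1. Replace the premedication sentence with: *Premedication may be given as described in Section 5.2.7; 5-HT3 antagonists are not allowed (Sections 5.2.4 and 5.2.12).* The exclusion has to be explicit because Section 5.2.7 allows equivalents.
2. Replace the contraception sentence with: *Women of child-bearing potential and men must use adequate contraception as required in Section 3.1.9: before study entry, throughout study participation, and for 4 months after onalespib administration is completed.* This keeps all three parts of the Section 3.1.9 requirement and the people it covers. It makes the two sections agree, but it carries over the undefined term, study participation.

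Notify sites that have patients on treatment or still within the Section 3.1.9 contraception period.

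The cost is two sentences and one site notice, with no change to sample size, error rates or any analysis.
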